## 10 STATISTICAL CONSIDERATIONS

### 10.1 Statistical and Analytical Plans

A formal statistical and analytical plan (SAP) will be completed prior to database lock and unblinding of the study data.

### 10.2 Statistical Hypotheses

The primary efficacy objective is to estimate the reduction of pain with EB-001, assessed as the difference in AUC for the NPRS pain scores over the 12-96 hours postsurgical period.

The null hypothesis is that the AUC for the EB-001 arm is greater than or equal to that of the placebo arm. The alternative hypothesis is that the AUC for EB-001 is smaller (indicating less pain) than that for placebo.

$$H_0: AUC_{EB-001} \geq AUC_{Placebo}$$

$$H_A: AUC_{EB-001} < AUC_{Placebo}$$

While not a formally powered study, a one sided hypothesis that the AUC for NPRS and NPRS-A will be used to inform the primary clinical hypothesis and support this objective.

### **10.3 Analysis Populations**

The modified Intent to Treat (mITT) population will include all randomized patients who receive study drug. All efficacy analyses will be performed using this population. Analyses will be performed on subjects using their randomized treatment group.

The Per Protocol (PP) population will include all subjects in the mITT population with no major protocol violations. The primary efficacy variable will also be analyzed using this population.

The Safety population will include all subjects exposed to any amount of study drug. All safety analyses will be performed using the safety population.

Analyses of using the PP and Safety populations will analyze subjects according to the treatment received. In the event that the subject receives the wrong treatment, they will be excluded from the per protocol population.

### **10.4 Description of Statistical Methods**

#### **10.4.1 General Approach**

Data will be summarized by dose of EB-001, across all subjects who received EB-001, and across all subjects who received placebo.

All continuous variables including oxygen saturation level documented every 2 hours will be summarized using descriptive statistics of mean, median, standard deviation, minimum, and maximum. Categorical variables will be summarized using descriptive statistics of number and percentage of patients in each category. The 95% confidence intervals may be shown as appropriate.

Statistical hypothesis testing will be performed, and one-sided p-values will be provided.

#### **10.4.2 Analysis of the Primary Efficacy Endpoint(s)**

The primary endpoint is the area under the curve (AUC) of subject's assessment of pain at rest using the Numeric Pain Rating Scale (NPRS) between 12 and 96-hour post-surgery ( $AUC_{12-96}$ ).

The primary endpoint will be analyzed using Analysis of variance (ANOVA) techniques with Treatment as the independent variable. Comparisons of the treatment arms to placebo will be performed using Dunnet's test. Additional covariates may be included in the model as exploratory analyses. Specifics of the analysis methodology and exploratory analyses will be defined in the SAP.

[figure not shown]
#### **10.4.3 Analysis of the Secondary Endpoint(s)**

Continuous secondary endpoints will be analyzed using similar methods as specified for the primary endpoint. Categorical endpoints (such as PGA) will be summarized and treatments compared using Fishers Exact, Chi-Square, or Cochran-Mantel- Haenszel techniques as appropriate. All secondary analyses will be specified in the detailed Statistical Analysis Plan (SAP).

## 10.5 Sample Size

Subjects will be allocated to receive either EB-001 or placebo in a 1:1 ratio in Cohorts 1-3, a 4:1 ratio in Cohort 4, a 2:1 ratio in Cohort 5, a 3:1 Ratio in Cohort 6, and a 5:1 ratio in Optional Cohort 7 in Stage 1 stratified by ethnicity (Hispanic and non-Hispanic) starting from Cohort 2. The planned total sample size in Stage 1 will be up to 40-58 subjects (up to 24-39 for EB-001 and up to 16-19 for placebo) (Figure 1). Optional Cohort 7 will be considered after dosing of subjects in Cohorts 1-6.

Subjects in each arm of Stage 2 will be randomly allocated to receive either EB-001 or placebo. The planned total sample size will be 66 subjects (44 for EB-001 and 22 for placebo) in Stage 2 stratified by ethnicity (Hispanic and non-Hispanic) (Figure 1).

Sample size of this study is not based on formal computations. However, 22 for active and 22 for placebo provide ~67% power. This power is based on one-sided alpha of 0.05, a mean baseline maximum pain score of 7.5, AUC12-96 ~440 with no drug effect, the delta AUC of 110 (drug and placebo difference), and SD of 170 AUC12-96.

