#### **Sample Size**

Subjects will be allocated to receive either EB-001 or placebo in a 1:1 ratio in Cohorts 1-3, a 4:1 ratio in Cohort 4, a 2:1 ratio in Cohort 5, a 3:1 Ratio in Cohort 6, and a 5:1 ratio in Optional Cohort 7 in Stage 1 stratified by ethnicity (Hispanic and non-Hispanic) starting from Cohort 2. The planned total sample size in Stage 1 will be up to 40-58 subjects (up to 24-39 for EB-001 and up to 16-19 for placebo) ([Figure 1](#)).

Subjects in each arm of Stage 2 will be randomly allocated to receive either EB-001 or placebo. The planned total sample size will be 66 subjects (44 for EB-001 and 22 for placebo) in Stage 2 stratified by ethnicity (Hispanic and non-Hispanic) ([Figure 1](#)).

Sample size of this study is not based on formal computations. However, 22 for active and 22 for placebo provide ~67% power to detect the difference. This power is based on one-sided alpha of 0.05, a mean baseline maximum pain score of 7.5, AUC12-96 ~440 with no drug effect, the delta AUC of 110 (drug and placebo difference), and SD of 170 AUC12-96.

Demographic and baseline characteristics will be summarized.

Safety will be assessed by summarizing the incidence of all adverse events, TEAEs, and serious adverse events in the Safety population. Other safety parameters (clinical laboratory parameters, vital signs, ECG measures, and pulmonary functions), including mean absolute change from baseline, will be summarized by treatment group.

The primary efficacy variable is the Area under the Curve (AUC) of subject's NPRS assessment between 12 and 96 hours post-surgery (AUC12-96). The primary efficacy variable will be summarized by treatment group. The Secondary Efficacy Measures include AUC assessment of overall pain profile using NPRS for various time duration. Secondary efficacy variables also include: NPRS at Days 6 through 29, NPRS-A over the first 96 hours and at Days 8, 15, 29, patient global assessment (PGA) of pain control, and use of rescue medications over various postsurgical periods. The statistical analyses for primary and secondary variables will be outlined in detail in the final SAP.

While this is not a formally powered study for efficacy analyses, efficacy data from the study will allow assessment of efficacy signal or trends, and exploration of the efficacious dose range. This will allow dose selection for future studies.

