## 10.6 Measures to Minimize Bias

### 10.6.1 Enrollment/ Randomization/ Blinding Procedures

Subjects who meet the enrollment criteria will be enrolled into sequential cohorts in Stage 1 or various arms in Stage 2. Subjects are considered to be randomly assigned to the study when they are assigned to receive either EB-001 or placebo. Subjects will be randomly allocated to receive either EB-001 or placebo stratified by ethnicity (Hispanic and non-Hispanic) starting from Cohort 2. In Stage 1, subjects in cohorts 1, 2, and 3 will receive active or placebo drug in a 1:1 ratio, in which subjects in the sentinel groups of these cohorts will receive active or placebo drug in a 1:2 ratio. Subjects in cohort 4 will receive active or placebo drug in a 4:1 ratio. Subjects in cohort 5 will receive active or placebo drug in a 2:1 ratio. Subjects in cohort 6 will receive active or placebo drug in a 3:1 ratio, in which subjects in the sentinel group will receive active or placebo drug in a 1:1 ratio. In the optional Cohort 7 of Stage 1, subjects will receive active or placebo drug in a 5:1 ratio.

In Stage 2, there will be 2 doses of EB-001 (to be determined by the SRC after last dosing of last subject of Stage 1) and placebo in a 1:1:1 ratio for a total of 66 subjects.

Each cohort will have a fixed dose of EB-001. The study in both stages will be conducted in a blinded manner (single-blind in Stage 1, double-blind in Stage 2). Study drugs between EB-

001 and the placebo vials will be identical in appearance. Study site personnel who prepare the study drug will not be involved in safety and efficacy assessment.

There will be an unblinded independent dispenser who will prepare and dispense EB-001 or placebo for administration in a blinded manner to subjects. The Investigator and site personnel, study subjects, and Sponsor personnel, unless otherwise specified, will be unaware of whether subjects are receiving EB-001 or placebo until the study is formally unblinded.

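### The ~67% power in Protocol 10.5 is that of one unadjusted two-group test; the planned Dunnett comparison of two doses has about 58% per dose on Stage 2 data alone

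*Protocol*

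**What the plan says.** Protocol 10.5 states that "22 for active and 22 for placebo provide ~67% power. This power is based on one-sided alpha of 0.05", and lists "the delta AUC of 110 (drug and placebo difference), and SD of 170 AUC12-96" among the inputs. The Sample Size part of the Protocol Summary gives the same figure: "22 for active and 22 for placebo provide ~67% power to detect the difference". Neither place names a test or mentions multiplicity.

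On the design, Protocol 10.6.1 states "In Stage 2, there will be 2 doses of EB-001" plus placebo, allocated 1:1:1. Protocol 10.5 gives the size: "The planned total sample size will be 66 subjects (44 for EB-001 and 22 for placebo) in Stage 2". That is 22 per arm.

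On the analysis, Protocol 10.4.2 fits an ANOVA with treatment as the factor and then says "Comparisons of the treatment arms to placebo will be performed using Dunnet's test". Protocol 10.4.1 makes p-values one-sided.

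Three statements limit the weight of the power figure:
- Protocol 10.5 and the Summary say that the sample size did not come from a formal calculation, and the Summary and 10.2 say that the study is not formally powered.
- The Clinical Hypothesis in the Protocol Summary asks for benefit at any one or more of the tested doses.
- SAP sections 1 and 3 drop all statistical comparisons because the study stopped early, after 23 subjects in Stage 1 (SAP 2.2).

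**The concern.** Anyone who reads 10.4.2 and 10.5 together will take ~67% as the power of the planned primary comparison. It is not. Dunnett's test spends the one-sided 0.05 across two dose comparisons, so each dose must clear a higher critical value than in a lone two-group test.

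What is at stake is how a negative Stage 2 comparison would be read, and whether the number is carried into a later design. At the protocol's own inputs, an effective dose would be missed about 42% of the time on Stage 2 data alone (100% minus 58%), not about a third of the time. The 0.05 in the power sentence is also not the level at which each dose would be tested. Testing both doses at an unadjusted one-sided 0.05 would give a familywise error of about 8.7%.

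**Working it through.** **Inputs.** Difference 110, SD 170, 22 per arm, one-sided alpha 0.05 (Protocol 10.5); two doses and placebo at 1:1:1 (10.6.1); Dunnett's test after ANOVA (10.4.2); one-sided p-values (10.4.1).

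**Step 1: reproduce the stated figure.** The standard error of a difference between two arms is 170 × √(1/22 + 1/22) = 51.26. The noncentrality is 110 / 51.26 = 2.146.
- Unadjusted one-sided t-test: df = 22 + 22 − 2 = 42, critical value 1.682. Power = P(noncentral t > 1.682) = 68.0%.
- Normal approximation: Φ(2.146 − 1.645) = 69.2%.
- Two-sided 0.05 (one-sided 0.025), t-test: 55.4%.

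Of these, the unadjusted one-sided t-test at 0.05 fits ~67%.

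**Step 2: Dunnett on Stage 2 data only.** The two test statistics share the placebo arm, so their correlation is 22 / (22 + 22) = 0.5. Variance is pooled over three arms: df = 66 − 3 = 63. The critical value c solves P(max(T1, T2) ≤ c) = 0.95 under the null. Numerical integration gives c = 1.950, and simulation gives 1.952.

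| Quantity | Power |
|---|---|
| A given dose: P(noncentral t, df 63, > 1.950) | 57.9% |
| At least one dose, both with difference 110 | 74.0% |
| Both doses, both with difference 110: 2 × 57.9% − 74.0%, before rounding | 41.9% |
| At least one dose, only one effective | 58.1% |

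Per-dose power is therefore about 10 points below the unadjusted 68.0% and about 9 below the stated 67%.

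**Step 3: sensitivity of the per-dose figure.** With an SD of 150 it is 69%, with 190 it is 49%, and with 200 it is 45%. At SD 170, a difference of about 122 would be needed for 67%. At a difference of 110, 27 to 28 per arm would be needed (66.8% and 68.4%).

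**Step 4: pooling Stage 1 placebo subjects.** Protocol 10.5 plans 16 to 19 of them, so the placebo group would be 22 + 16 = 38 or 22 + 19 = 41, still with two doses of 22.
- 38 placebo: standard error 170 × √(1/22 + 1/38) = 45.54; noncentrality 2.415; correlation 22/60 = 0.367; df = 82 − 3 = 79; critical value 1.960; power 67.6% per dose.
- 41 placebo: standard error 44.93; noncentrality 2.448; correlation 22/63 = 0.349; df = 85 − 3 = 82; critical value 1.961; power 68.7% per dose.

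If Stage 1 doses also entered the ANOVA as arms, there would be more comparisons and the figure would change again.

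**The case against.** The strongest defence has four parts.

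**The sentence describes what it computes.** It names two groups of 22 and an alpha, and the number follows from them to within a point. That stands: a reader might infer an arithmetic error, and there is none. The fault is that the test is not named and is not the one planned in 10.4.2.

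**The protocol disclaims formal powering.** This also stands, and it lowers the severity. But the disclaimer explains how the 66 subjects were arrived at. It does not make a quoted power figure apply to a different test.

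**58% is not the only relevant power, and it is conditional.** A reader might infer that true power is simply lower than stated. The documents do not support that without qualification. The clinical hypothesis is met by success at any dose, and for that criterion power is 74% if both doses work, above the stated figure; it falls to about 58% if only one works. Also, 10.4.2 does not restrict the ANOVA to Stage 2, and 10.4.1 summarises across all placebo subjects. Pooling the Stage 1 placebo subjects brings per-dose power back to about 67-69%. So 58% has to be given with its assumption.

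**Nothing in the trial turns on it.** A reader might infer that a go/no-go or dose-choice decision rested on the 67%. No section states such a rule; the Summary ties future dose selection to the efficacy data, not to power. The SAP, which is based on Amendment 3, cancels testing altogether. The Stage 2 design, Dunnett's test and the power statement remain current text in the protocol that incorporates Amendment 4, so the planning record is still worth correcting.

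**Conclusion.** The point holds as a mismatch between the stated power and the planned test. The ~67% belongs to one unadjusted one-sided two-group comparison. For the Dunnett comparison of two doses with placebo, power is about 58% for a given dose and, if both doses have a difference of 110, about 74% for at least one and 42% for both.

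These figures assume Stage 2 data only, 22 per arm with no loss, SD 170, 0.05 as the familywise one-sided level, and variance pooled over three arms.

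Severity is minor to moderate. The fault lies in a planning statement; it affects no reported test, and it gives no ground for saying that the trial's size was wrongly derived.

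**What to change.** In Protocol 10.5 and in the Sample Size part of the Protocol Summary:
- Label ~67-68% as the power of a single unadjusted one-sided comparison of 22 against 22.
- Add that, under one-sided Dunnett at familywise 0.05 with Stage 2 data only, power is about 58% for a given dose, and about 74% for at least one dose and 42% for both if both have a difference of 110 with SD 170.
- State in 10.4.2 whether Stage 1 subjects enter the ANOVA. If Stage 1 placebo subjects are to be pooled, restate the per-dose figure (about 67-69% with 16 to 19 added).

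The cost is about two sentences in each place and one clause in 10.4.2. The sample size does not change. The quoted power becomes less favourable per dose on the Stage 2-only basis, though not for success on at least one dose when both work.

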## 10.6 Measures to Minimize Bias

### 10.6.1 Enrollment/ Randomization/ Blinding Procedures

Subjects who meet the enrollment criteria will be enrolled into sequential cohorts in Stage 1 or various arms in Stage 2. Subjects are considered to be randomly assigned to the study when they are assigned to receive either EB-001 or placebo. Subjects will be randomly allocated to receive either EB-001 or placebo stratified by ethnicity (Hispanic and non-Hispanic) starting from Cohort 2. In Stage 1, subjects in cohorts 1, 2, and 3 will receive active or placebo drug in a 1:1 ratio, in which subjects in the sentinel groups of these cohorts will receive active or placebo drug in a 1:2 ratio. Subjects in cohort 4 will receive active or placebo drug in a 4:1 ratio. Subjects in cohort 5 will receive active or placebo drug in a 2:1 ratio. Subjects in cohort 6 will receive active or placebo drug in a 3:1 ratio, in which subjects in the sentinel group will receive active or placebo drug in a 1:1 ratio. In the optional Cohort 7 of Stage 1, subjects will receive active or placebo drug in a 5:1 ratio.

In Stage 2, there will be 2 doses of EB-001 (to be determined by the SRC after last dosing of last subject of Stage 1) and placebo in a 1:1:1 ratio for a total of 66 subjects.

Each cohort will have a fixed dose of EB-001. The study in both stages will be conducted in a blinded manner (single-blind in Stage 1, double-blind in Stage 2). Study drugs between EB-

001 and the placebo vials will be identical in appearance. Study site personnel who prepare the study drug will not be involved in safety and efficacy assessment.

There will be an unblinded independent dispenser who will prepare and dispense EB-001 or placebo for administration in a blinded manner to subjects. The Investigator and site personnel, study subjects, and Sponsor personnel, unless otherwise specified, will be unaware of whether subjects are receiving EB-001 or placebo until the study is formally unblinded.

#### **10.6.1.1 Subject Numbering**

Patients who have signed the ICF to begin screening procedures will be entered into the electronic data capture (EDC) system. The site will assign a 3-digit site-specific sequential screening number at that time. The unique patient identification number will consist of a 3-digit original site number followed by a 3-digit screening number. The patient will keep the same number throughout the study. Upon randomization, a unique 4-digit study-specific randomization number will be assigned.

In the circumstance, where a patient is randomly assigned to treatment but does not receive the study drug, the study coordinator/research nurse must immediately inform the unblinded CRA that the study drug was not administered.

#### **10.6.2 Evaluation of Success of Blinding**

##### **10.6.2.1 Blinding at the Study Site**

Study treatment group information (active drug vs placebo) will remain blinded to the subject and also to all blinded members of the study team at the study site. There will be an unblinded independent dispenser who will prepare and dispense EB-001 or placebo for administration in a blinded manner to subjects. Study site personnel who prepare the study drug will not be involved in safety and efficacy assessment.

Investigators, coordinators, and nurses who are responsible for reviewing potentially unblinded medical data or who may have access to it (including all routine laboratory tests, imaging, and AEs) must not discuss any unblinded information or results with the site personnel responsible for blinded study assessments.

##### **10.6.2.2 Blinding/Unblinding of Sponsor Personnel**

During this study, staff of Bonti and designee will be unblinded to treatment allocation in Stage 1, and blinded to treatment allocation in Stage 2, except as described in this section and in the Site Blinding Plan. The periodic SRC reviews will be performed in a blinded manner unless the data warrant unblinding due to safety concerns. It is assumed that the need to unblind a study subject's treatment assignment will occur in the setting of an SAE, and therefore, all procedures for the reporting of a SAE must be followed (see [Section 8.5.1](#)).

Procedures for emergency unblinding are described in [Section 10.6.3](#). These procedures ensure that neither study blinded monitoring staff nor the Investigator and other site staff who are blinded have premature access to the study subjects' treatment assignments. Upon notification of an unblinding event, the Sponsor will assess the need for potentially removing the unblinded personnel from the trial.

### **10.6.3 Breaking the Study Blind/Participant Code**

An Investigator at a site may break the blind in the event of an immediate medical emergency, where knowledge of the study subject's treatment assignment (EB-001 or placebo) must be known in order to facilitate appropriate emergency medical treatment. In these situations, the Investigator must first attempt to contact the Medical Monitor or designee before unblinding a subject's treatment identity in order to obtain concurrence that unblinding a study subject's treatment assignment is necessary. If circumstances preclude contacting the Medical Monitor or designee, each instance of unblinding must be reported to Sponsor within 24 hours. The Medical Monitor or designee may break the blind internally in the event of SAE(s), which require expedited reporting to regulatory authorities. Any other requests to reveal a subject's treatment identity must be requested of, and approved by the Medical Monitor or designee. If a study subject's treatment identity is unblinded by the study site, the unblinding must be reported to Bonti and documented on the eCRF as a deviation. Upon notification of an unblinding event, the Sponsor will assess the need for potentially removing the unblinded personnel from the trial. If a subject's treatment identity is unblinded, the subject will be withdrawn from the study and will complete the Early Termination procedures describe in [Section 5.4](#).

In an emergency situation in which the Investigator believes that the identity of a study subject's treatment assignment is necessary to treat the subject, the study subject's treatment assignment may be obtained from the randomization list. Details of the process to be followed are provided in the study manual(s) provided to the site. In the event that the treatment assignment is unblinded, Bonti or designee will be notified immediately that the blind has been broken, but will not be informed of the actual treatment assignment of the subject unless required for SAE reporting or other specific reason. Other study team personnel will remain blinded unless unblinding is necessary for the safety of the subject.

The Investigator or designee is responsible for ensuring that the instructions on how to perform a code break are stored safely, that their location is known, and that access is readily available to the relevant staff in case of an emergency.

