## 4 STUDY DESIGN AND ENDPOINTS

### 4.1 Description of the Study Design

This will be a two-stage study. The study will be conducted at up to two surgical centers that specialize in elective abdominoplasty surgeries and enroll up to 39-57 subjects in Stage 1 and 66 subjects in Stage 2 ([Figure 1](#)), with up to 67-82 subjects exposed to active drug. The study will include a screening visit to determine subject eligibility. On the day of surgery, subjects will be admitted to an inpatient clinic for 5 days post-operatively (Days 1-5) ([Table 1](#) and [Table 2](#)). Intraoperatively, a single dose of EB-001 IM will be given via IM injections into the RA muscles per the surgical procedure manual. Follow up visits will be scheduled at days 8, 15, and 29.

The first stage will be a placebo controlled, single-blind (to subject and staff at study sites), single ascending cohort study stratified by ethnicity (Hispanic and non-Hispanic) starting from Cohort 2. Six cohorts (3-8 subjects per cohort) will be dosed at 6 ascending doses of EB-001. An optional Cohort 7 may be considered.

Cohort 1 sentinel group (3 subjects; 1 active: 2 placebo) [REDACTED] The rest of the cohort (5 subjects; 3 active: 2 placebo) will be dosed at the same dose after review of all available data by the Safety Review Committee (SRC) is conducted, with safety data through at least Day 5 post-operatively.

Cohort 2 sentinel group (3 subjects; 1 active: 2 placebo) [REDACTED] after review of all available safety data from the prior cohort through at least Day 5 post-operatively. The rest of the cohort (5 subjects; 3 active: 2 placebo) will be dosed after review of all available data by the SRC is conducted, with safety data through at least Day 5 post-operatively.

Cohort 3 sentinel group (3 subjects; 1 active: 2 placebo) [REDACTED] after review of all available safety data from the prior cohorts through at least Day 5 post-operatively. The rest of the cohort (5 subjects; 3 active: 2 placebo) will be dosed after review of all available data by the SRC is conducted, with safety data through at least Day 5 post-operatively.

Cohort 4 group (5 subjects; 4 active: 1 placebo) [REDACTED] after review of all available safety data from the prior cohort through at least Day 5 post-operatively.

Cohort 5 group (3 subjects; 2 active: 1 placebo) [REDACTED] after review of all available safety data from the prior cohort through at least Day 5 post-operatively.

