### 5.4.2 Handling of Participant Withdrawal or Termination

If a subject discontinues from the study prematurely, all efforts will be made to conduct early termination (ET) evaluations as thoroughly as possible up to the date of withdrawal at the time of discontinuation.

Subjects who discontinue participation, or who are discontinued prior to completing study participation, will be asked to complete ET procedures, including:

- Assessment of AEs
- Assessment of AEs of Special Interest including post-operative dyspnea, tachypnea, tachycardia, pneumonia, atelectasis, and fever
- Height, weight, and BMI
- Mini-physical and focused neurological examinations
- Prior and concomitant medications
- 12-lead ECG
- Body temperature, respiration rate, blood pressure, pulse oximetry, and pulse rate
- Serum chemistry, Lipids, and Hematology
- Urinalysis
- Immunogenicity sample collection
- Pregnancy test
- Postoperative wound assessment

- Overall assessment of pain at rest using NPRS (if prior to the 96-hr assessment)
- Pain assessment using NPRS-A after sitting up in the bed unassisted at an angle of approximately 45 degrees or more, swinging legs out, putting feet down, standing up, and walking approximately 10 feet (if prior to the 96-hr assessment)
- Patient global assessment (PGA) of pain control
- Pulmonary function test (SVC, FVC, and FEV1)
- Use of rescue medications
- Collection of take-home diaries (if applicable)

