#### **5.4.3 Handling of Participant Exceeding Allowed Rescue Medication**

Subjects who exceed limit of allowed rescue medication, considered noncompliance with the protocol specified in [Section 5.4.1](#) due to lack of efficacy, will be followed, not early terminated, with regard to all safety assessments per protocol. They at all subsequent visits will be asked to complete protocol-specified assessments, with the exception of efficacy assessments as follows:

- NPRS
- NPRS-A
- Collection of take-home pain assessment diary

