7. EFFICACY EVALUATION

7.1 Overview of Efficacy Analysis Issues

7.1.1 *Handling of Dropouts or Missing Data*

If a subject receives protocol specified rescue medication, a windowed LOCF imputation method will be used and the pre-rescue pain NPRS/NPRS-A score for each assessment (pain at rest, pain after walking) will be carried forward for 4 hours. Intermittent missing pain scores (due to subject sleeping, etc.) will not be imputed, and AUC will be calculated based on non-missing values.

In AUC analyses, no other imputation will be performed for subjects who have missing values due to early drop out. In addition, there will be no imputation of missing data for safety or other efficacy assessments.

7.1.2 *Assessment Time Windows*

Assessment times will be based on the nominal protocol-specified assessment times.

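### Breaking the code withdraws a subject whose single dose is already given: later scheduled safety visits are lost, and a break before 96 h can leave the pain AUC too low

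*Protocol*

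**What the plan says.** Protocol Section 10.6.3 states the rule without exception. Once a treatment identity is unblinded, "the subject will be withdrawn from the study and will complete the Early Termination procedures". The same section lets the Medical Monitor break the blind internally for expedited reporting, and the withdrawal sentence does not exempt that case.

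The related text is:

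- **Treatment** (Protocol 4.1): "Intraoperatively, a single dose of EB-001 IM will be given via IM injections into the RA muscles per the surgical procedure manual".
- **When codes are broken** (Protocol 10.6.2.2): "It is assumed that the need to unblind a study subject's treatment assignment will occur in the setting of an SAE".
- **Early termination** (Protocol 5.4.2): evaluations are made "as thoroughly as possible up to the date of withdrawal at the time of discontinuation".
- **Later visits** (Protocol 4.1): "Follow up visits will be scheduled at days 8, 15, and 29".
- **Subjects over the rescue limit** (Protocol 5.4.3): they "will be followed, not early terminated, with regard to all safety assessments per protocol", but NPRS, NPRS-A and the pain diary are dropped.
- **AUC** (SAP 4.1, 7.1.1, 7.3.1): trapezoids are summed in score-hours over non-missing values and not divided by observed time. Beyond the 4-hour carry-forward after rescue, "no other imputation will be performed for subjects who have missing values due to early drop out". One NPRS score between 12 and 96 h is enough to enter mITT.

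**The concern.** After a single dose there is no treatment left to stop, so mandatory withdrawal only ends observation. It does so in subjects whom the protocol expects to have had an SAE, and they then get less scheduled safety follow-up than subjects who merely took too much rescue medication. Read literally, the rule also removes a subject whose code was opened only inside the sponsor, although subject and site may still be blind.

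The second effect comes from the SAP. When scores stop inside the 12-96 h window, the missing hours add nothing to the sum. A subject withdrawn after an emergency is then recorded as having had less pain. Treatment-group summaries of AUC12-96 and the listed individual values would carry that error.

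**Working it through.** **1. The plan's own figure.** Protocol 10.5 gives 22 per arm, one-sided alpha 0.05, AUC12-96 of about 440 without drug effect, a difference of 110 and an SD of 170, with about 67% power. The standard error is 170 × √(2/22) = 51.3 and the noncentrality is 110/51.3 = 2.15. A two-sample t-test with 42 df then gives 68.0%, which reproduces the stated figure to about one point (normal approximation: 69.2%).

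**2. Pain profiles (assumed).** The documents give no profile shape, so two are used, each with a full AUC of 440 over 84 h:
- Flat: 440/84 = 5.24 throughout.
- Declining in a straight line from 7.5 at 12 h (the maximum score in Protocol 10.5) to 2 × 440/84 − 7.5 = 2.98 at 96 h. The slope is (2.98 − 7.5)/84 = −0.0539 per hour.

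**3. AUC when scores stop at hour w.** Flat: 5.238 × (w − 12). Declining: (w − 12) × [7.5 + s(w)]/2, with s(w) = 7.5 − 0.0539 × (w − 12). For example, at 48 h: flat 5.238 × 36 = 188.6; declining 36 × (7.5 + 5.56)/2 = 235.1.

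| Withdrawal | AUC flat / declining | Shortfall from 440 | Shift of mean, n = 4 | Shift of mean, n = 22 |
|---|---|---|---|---|
| 24 h | 62.9 / 86.1 | 377 / 354 | 94 / 88 | 17.1 / 16.1 |
| 48 h | 188.6 / 235.1 | 251 / 205 | 63 / 51 | 11.4 / 9.3 |
| 72 h | 314.3 / 353.1 | 126 / 87 | 31 / 22 | 5.7 / 4.0 |
| 94 h | 429.5 / 433.9 | 10.5 / 6.1 | 2.6 / 1.5 | 0.5 / 0.3 |
| 96 h or later | 440 / 440 | 0 | 0 | 0 |

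The shift is the shortfall divided by n. Four is the number of active subjects per dose in Cohorts 1-3; 22 is a Stage 2 arm. The shortfall scales with the subject's full AUC: at 440 − 110 = 330, each entry is three quarters of the one shown.

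**4. Edge cases.** With a single in-window score, at 12 h, the AUC is 0 and the subject is still in mITT. With no in-window score the subject is outside mITT and has no primary AUC.

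**5. Safety follow-up after the break.**

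| Item | After withdrawal |
|---|---|
| Early termination tests, including neurological examination, pulmonary function, laboratory, ECG and immunogenicity (Protocol 5.4.2) | Done once |
| Known AEs and SAEs (Protocol 8.3, 8.5, 8.5.1) | Followed on |
| Questioning for new AEs at each study visit (Protocol 8.3) | No further scheduled visits |
| Day 8, 15 and 29 assessments still to come | Not required |

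Two details show what may be missed. The SVC criterion in Protocol Table 4 counts only values at 96 h or later with a confirming repeat, so a subject withdrawn earlier has no required measurement that could meet it. The text after Table 3 expects recovery from systemic toxicity to begin about one week after dosing, which is when the follow-up visits start.

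**The case against.** Several points on the other side stand in whole or part.

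- **Safety follow-up is not simply lost.** A reader might infer that it is. The early termination list is broad, known AEs and SAEs are followed, and Protocol 8.5.1 asks for later SAEs if causation is reasonably possible. SAP 4.3 has a category for subjects who discontinue but agree to safety follow-up, although that is a reporting category and obliges nobody to follow them. What goes is the later scheduled assessments and systematic capture of new events.
- **Not every unblinded subject gets a low AUC.** A reader might infer this too. It needs withdrawal before 96 h and at least one in-window score. A break prompted by the Table 4 SVC criterion, which applies from 96 h, leaves AUC12-96 intact.
- **A bias favouring active drug is not shown.** Toxin-type events might make code breaks commoner on active drug, but the documents give neither a rate nor a split by arm.
- **Section 5.4.3 is a precedent for safety follow-up only.** It drops pain scores. Not collecting self-reported pain after the blind is broken is a defensible choice. The case for continuing NPRS rests on the AUC derivation, not on 5.4.3.
- **The AUC weakness belongs to the SAP.** It affects every early drop-out, and changing 10.6.3 cures it only for code breaks.
- **No planned test is biased.** SAP Sections 1 and 2.2 report termination after 23 subjects in Stage 1 and allow no statistical comparisons. The 22-subject arms were not run.

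**Conclusion.** The point holds in a limited form. Automatic withdrawal after a code break serves no treatment purpose here. It ends the remaining scheduled safety visits in subjects likely to have had an SAE, and it is out of line with Section 5.4.3. That conclusion needs no arithmetic.

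The AUC effect is conditional on a break before 96 h with an in-window score. It can then be large for the individual: at 48 h the shortfall of 205-251 is about twice the planned difference of 110 (1.9 to 2.3 times). For a 4-subject dose-group mean it is about half that difference (51-63). For a 22-subject arm it is 9-11, or 8% to 10%. These sizes rest on the two assumed profiles, on one affected subject and on a full AUC of 440. How often this would happen, and in which arm, cannot be derived from the documents. What is exposed is descriptive summaries and listings. The SAP is also written to Amendment 3, while the protocol text carries Amendment 4.

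**What to change.** Replace the withdrawal sentence in Protocol 10.6.3 with wording such as:

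> Subjects whose treatment identity is unblinded remain in the study and complete all scheduled safety assessments to Day 29 unless they withdraw consent. NPRS collection continues to 96 h, with post-unblinding scores flagged. The unblinding is recorded as a deviation.

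Reconcile it with Protocol 5.4.3, 8.5 and 8.5.1 and with SAP 4.3. The change concerns data collection only; clinical management of the subject is untouched.

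In the SAP, keep these subjects in mITT and add a sensitivity analysis that either excludes them or uses a time-normalised AUC, that is, AUC divided by observed hours, times 84. The second option can overshoot when pain is falling: at 48 h it gives 188.6/36 × 84 = 440 for the flat profile but 235.1/36 × 84 = 549 for the declining one. A raw AUC cut at unblinding should not be used, because it recreates the shortfall. If scoring continues to 96 h, the full 440 is recovered under both profiles.

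The cost is one protocol sentence, the cross-reference edits and a short SAP paragraph. The downside is that pain scores after the break are no longer blinded, which is why they are flagged and examined separately.
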